Table 9	Movement Disorder Society (MDS) Diagnostic Criteria for Clinically Established Parkinson's Disease.....	61
Table 10	Parkinson's Disease Criteria per Hoehn and Yahr (1967)	61
Table 11	ALS Diagnostic Criteria.....	64

STATEMENT OF COMPLIANCE

The study will be carried out in accordance with International Council for Harmonization Good Clinical Practice (ICH-GCP) and the following:

- United States (US) Code of Federal Regulations (CFR) applicable to clinical studies (45 CFR Part 46, 21 CFR Part 50, 21 CFR Part 56, 21 CFR Part 312, and/or 21 CFR Part 812)

The protocol, informed consent form(s), recruitment materials, and all subject materials will be submitted to the Institutional Review Board (IRB) for review and approval. Approval of both the protocol and the consent form must be obtained before any subject is enrolled. Any amendment to the protocol will require review and approval by the IRB before the changes are implemented to the study, unless the protocol change is intended to eliminate an apparent immediate hazard to subjects. In addition, all changes to the consent form will be IRB-approved; a determination will be made regarding whether a new consent needs to be obtained from subjects who provided consent, using a previously approved consent form.

1 PROTOCOL SUMMARY

1.1 SYNOPSIS

Title: Prospective Randomized Open, Blinded Endpoint (PROBE) Study of AMDX-2011P as a Retinal Tracer in Subjects with Neurodegenerative Diseases Associated with Amyloidogenic Proteinopathy

Study Phase: Phase 1/2a

Study Description: AMDX-2011P is a novel retinal tracer in clinical development for the detection of neurodegenerative diseases associated with amyloidogenic proteinopathy by detecting alpha-synucleinopathies (α -syn) in Parkinson's disease, and transactive response DNA-binding protein 43 (TDP-43) in amyotrophic lateral sclerosis (ALS). Nonclinical studies have demonstrated that AMDX-2011 binds selectively to protein with high beta sheet content, such as retinal α -syn and TDP-43 deposits, enabling visualization through conventional retinal imaging. There is currently a significant need for an accessible diagnostic measure to facilitate early diagnosis and patient management in these conditions.

The current prospective randomized open, blinded endpoint (PROBE) study will evaluate the activity, safety, tolerability, and pharmacokinetics (PK) as well as detect amyloidogenic deposits through retinal imaging following escalating doses of bolus intravenous (IV) AMDX-2011P administration in subjects with Parkinson's disease, multiple system atrophy (MSA) and ALS. Assessments of retinal images will be conducted by central masked assessors in a randomized fashion.

Objectives and Endpoints:

OBJECTIVES	ENDPOINTS
Primary	

 To assess safety and tolerability of single IV dose of AMDX-2011P in subjects with neurodegenerative diseases (Parkinson's disease, MSA and ALS). 	
 Incidence, nature, and severity of adverse events (AEs) and serious adverse events (SAEs).
Secondary	

 To assess the ability of AMDX-2011P to identify α-syn in retina of subjects with Parkinson's disease or MSA. 	
 Detection of α-syn in the retina after AMDX-2011P administration.

 To assess the ability of AMDX-2011P to identify TDP-43 in retina of subjects with ALS. 	
 Detection of TDP-43 in the retina after AMDX-2011P administration.

 To characterize the PK profile of AMDX-2011P and AMDX-2011 following administration of a single IV dose of AMDX-2011P in subjects with neurodegenerative diseases (Parkinson's disease, MSA and ALS). 	
 PK parameters of AMDX-2011P and AMDX-2011 calculated from concentrations in plasma.

Overall Study Design

This is a PROBE study designed to evaluate the safety, tolerability, and the ability of AMDX-2011P to detect amyloid deposits, α -syn and TDP-43 (collectively called amyloidogenic deposits) through retinal imaging, as well as PK of single bolus IV of AMDX-2011P in subjects with Parkinson's disease, MSA and ALS. Study schema is shown in Section 1.2.

The study will enroll up to 4 dose cohorts as follows:

Cohort	Number of Subjects with neurodegenerative diseases (Parkinson's Disease and/or MSA and/or ALS) ^a	Proposed dose level
1	3-9 ^b	25 mg (1 mL)
2	3-9 ^b	50 mg (2 mL)
3	12 ^b	100 mg ^c (4 mL)
4	12 ^b	150 or 200 mg ^c (6-8 mL)

Abbreviation: ALS, amyotrophic lateral sclerosis; SMC, Safety Monitoring Committee; TBD, to be determined.

a. Additional subjects (from any subject population) may be enrolled into any cohort per SMC discretion. Approximately 12 ALS subjects will be enrolled in the study.

b. All cohorts will include 1 sentinel subject who will be observed for 8 hours and evaluated at 24 hours for safety before enrolling the remaining subjects in that cohort.

c. Tentative dose and will be confirmed by SMC based on emerging data from the prior cohorts; intermediate or higher dose level may also be explored in these cohorts

A Safety Monitoring Committee (SMC), comprised of the Study Medical Monitor (or designee), neurologists with experience in these patient populations, an ophthalmologist with retinal imaging expertise, and the Sponsor's clinical and technical representatives, will review safety data throughout the study. The SMC may recommend modifying the duration

of observation or timing of study procedures based on safety and other available data from the prior cohorts.

All cohorts will include subjects with neurodegenerative diseases (Parkinson's disease, MSA and/or ALS). The decision to escalate to the next dose level will be made based on review of all available safety and tolerability data collected including AEs, electrocardiograms (ECGs), vital signs, and laboratory safety results of the previous dose levels after single dose administration in at least 3 subjects from each cohort. Based on emerging data, additional cohort(s) and/or an intermediary dose may be investigated with prior approval by the SMC. The study may progress to the next cohort if approved upon satisfactory review of available safety data of the previous cohort(s) by the SMC. During each safety review, the SMC will make a decision to either continue enrollment to the next planned cohort, add additional subjects to the current cohort, or change the dose of the next cohort.

Enrollment into each cohort will begin with 1 sentinel subject who will be observed for at least 8 hours at the clinic and evaluated by the investigator at 24 hours following dosing by the investigator. If no safety issues are observed, the remaining subjects will be enrolled into that cohort. Dosing of remaining subjects at the same center will be staggered by at least 1 hour. Dosing within a cohort will continue unless stopping rules are met.

[figure not shown]
For all dose cohorts, after signing the informed consent, subjects will be screened. If needed, the screening procedures may occur over a period of up to 42 days prior to dosing. On Day 1, subjects will be admitted to the clinical research unit for 8 hours confinement. Eye examination and retinal imaging will be conducted before administration of the study drug.

AMDX-2011P will be administered through a single IV bolus injection followed by repeated retinal imaging and PK and safety assessments as outlined in the Schedule of Activities (SoA; Section 1.3). On Day 8 (end of study), there will be a follow-up visit for retinal imaging and safety assessments.

All retinal images will be deidentified and sent in batches to a reading center for masked assessment. Assessors will be masked to type of subjects, their disease, dose, clinical status of subjects, and sequence of post-injection images. This provides an objective assessment of the ability of AMDX-2011P to identify amyloidogenic deposits. During the interim analysis, the SMC may also review representative images to confirm the optimum detection and the residence time and make potential recommendations to the retinal imaging time point(s) and/or potential safety assessment modifications.

Study Population:	Adult subjects with neurodegenerative diseases: Up to 36 adult male and female subjects diagnosed with Parkinson's disease, MSA or ALS.
Description of Sites/Facilities	The study will be conducted at 4-5 Phase 1 ophthalmology experienced sites located in the United States.
Enrolling Subjects:	
Description of Study drug:	AMDX-2011P is a novel retinal tracer indicated for the diagnosis of amyloid angiopathy. It is a phosphate prodrug hydrolyzed in vivo to the pharmacologically active molecule AMDX-2011.
Study Duration:	Estimated time to complete study from enrollment to completion of data analyses will be 7 months.
Subject Duration:	For each subject, study participation is expected to last up to 8 days: one day of dosing, 7 days of follow-up, and a window of up to 42 days to complete the screening procedures.

1.2 SCHEMA

Abbreviations: SMC, Safety Monitoring Committee.

1.3 SCHEDULE OF ACTIVITIES (SoA)

Table 1 Schedule of Activities (Subjects with Neurodegenerative Diseases, All Dose Cohorts)

Study Procedures	Screening ¹	Treatment	Follow-up	Notes
Study Visit	-42 to -1	Day 1	Day 8/EOS/ET	
Visit window (days)	42		+2	
Informed consent	X			
Domiciled		X ^a		a. Subjects will be admitted to the clinical research unit in the morning for 8 hours confinement
Medical/ocular history/Physical exam	X			On Day 1, PE may be repeated if abnormalities are detected at screening. Relevant ocular and disease-specific history will be captured up to date of diagnosis.
Eligibility (inclusion/exclusion criteria)	X			
Body weight and Height	X			
Eye examination/	X	X	X	Refer to Section 8.1.1.
Color fundus photography	X			
Vital signs	X	X ^b	X	b. To be collected predose, and at 0.25, 0.5, 1, 2, 8 hours postdose. A window of \pm 5 minutes will be allowed for measurements up to 2 hours, and \pm 10 minutes beyond 2 hours.
12-lead safety (ECG)	X	X ^c	X	c. Triplicate at the following timepoints: predose (within 1 hour), and at 90 minutes (\pm 15 minutes) and 8 hours (\pm 60 minutes) postdose or before discharge
Safety laboratories	X	X ^d	X	Refer to Section 10.2. d. To be collected predose on Day 1 and before discharge
Urinalysis	X	X	X	
Pregnancy test	S	U (predose)	U	S = Serum; U = Urine
Adverse event reporting	X	X	X	

Study Procedures	Screening ¹	Treatment	Follow-up	Notes
Study Visit	-42 to -1	Day 1	Day 8/EOS/ET	
Visit window (days)	42		+2	
Concomitant medications	X	X	X	
Retinal fundus fluorescence (FF) imaging		X ^e	X	e. Refer to Section 8.1.2
Retinal optical coherence tomography (OCT) and OCT angiography (OCTA)	X		X	
Blood PK sampling		X ^f		f. On Day 1, PK blood samples will be collected at the following time points: 0 (predose), and at 3, 6, 15, and 30 minutes postdose and 1, 2, 4, 6, and 8 hours postdose. A window of ± 5 minutes will be allowed for samples collected from 30 minutes to 2 hours, and ± 10 minutes beyond 2 hours.
Study drug administration		X		

Abbreviations: AE, adverse events; ECG, electrocardiogram; EOS, end of study; ET, early termination; FU, follow-up; PE, physical examination; PK, pharmacokinetics.

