The safety of AMDX-2011P has been evaluated in a program of Good Laboratory Practice (GLP) toxicology and safety pharmacology studies, conducted using a single bolus IV injection of AMDX-2011P to mimic the clinical dosing regimen. In the definitive GLP single-dose rat study, no adverse target organ toxicity and no evidence of ocular or cutaneous phototoxicity were identified at up to 50 mg/kg. Injection site reactions occurred in rats after administration into the tail vein, which were considered adverse at 50 mg/kg and not adverse at \leq 15 mg/kg. Therefore, in rats, the dose showing no adverse systemic toxicity was 50 mg/kg, and the overall study no-observed-adverse-effect level (NOAEL) was 15 mg/kg. In safety pharmacology studies conducted in rats, there were no acute neurobehavioral changes or effects on respiratory function at up to 50 mg/kg. In the definitive GLP single-dose dog study, reversible clinical ophthalmic signs, including mydriasis, minimal hyperemic conjunctiva and minimal to mild chemosis, occurred in male dogs within 24 hours postdose at 60 mg/kg. Other non-adverse clinical signs at 60 mg/kg included intermittent emesis and soft feces, which resolved by Day 2 and were not considered adverse. There was histologic evidence of injection site reactions in dogs at all doses, which were not considered adverse. There was no adverse target organ toxicity in dogs at 60 mg/kg, which was considered the NOAEL in females; the NOAEL in males was 20 mg/kg.

based on ophthalmic changes at 60 mg/kg. In a dog cardiovascular safety study, transient reductions in blood pressure (systolic, diastolic, and mean arterial pressure) and heart rate occurred at 15-30 minutes after a single bolus injection of 30 mg/kg, but not at \leq 10 mg/kg, and there were no effects on electrocardiogram (ECG) profile at any dose. In vitro, AMDX-2011 caused a dose-dependent inhibition of the human Ether-à-go-go-related gene (hERG) cardiac potassium channel of up to 44% at a concentration of 10 μ M. This concentration is expected to be at least 10-fold above human peak plasma concentration (C_{max}) values of the pharmacologically relevant doses; therefore, a risk for QTc prolongation in humans is considered low. Overall, the nonclinical safety studies support the safe administration of AMDX-2011P in this study.

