4.3 JUSTIFICATION FOR DOSE

The proposed starting dose is based on recommendations from an FDA Guidance for Industry: *Estimating the Maximum Safe Starting Dose in Initial Clinical Trials for Therapeutics in Adult Healthy Volunteers, July 2005* (FDA, July 2005). Table 4 shows NOAEL doses and systemic AUC and C_{max} exposures from the pivotal rat and dog toxicity studies, as well as projected human exposures at proposed clinical dose levels. Clinical PK parameters (clearance and volume of distribution) for AMDX-2011P were projected by model fitting of dog PK data, then scaling to human values. AMDX-2011 parameters were projected based on rates of formation and

observed metabolite/parent ratios in animals. Human PK profiles were then simulated at various doses based on projected parameter values.

The lowest NOAEL for dogs (20 mg/kg, males) equates to a human equivalent dose (HED) for a 60-kg adult male of 667 mg, and the NOAEL for systemic toxicity in rats (50 mg/kg) equates to a HED of 484 mg. Using an ~20-fold safety margin, the starting dose in the proposed clinical study will be 25 mg. The escalating doses will be 25 mg, 50 mg, 100 mg, and either 150 mg or 200 mg.

The doses proposed for this study will cover the anticipated pharmacologically active dose range and are predicted to be significantly below AUC and C_{max} exposures for AMDX-2011 and AMDX-2011P achieved at NOAEL doses in rats and dogs.

Table 4 Projected Human Dose Levels and Corresponding AUC and C_{max} Exposures Based on Nonclinical Data

Dose	AUC (hr •ng /mL)		C_{max} (ng/mL)	
	AMDX-2011P^a	AMDX-2011^a	AMDX-2011P^a	AMDX-2011^a
Human (mg)				
25	49.0	19.1	135	43.8
50	97.8	38.2	269	87.5
75	144	57.4	403	131
100	192	76.6	539	175
150	288	115	806	263
200	383	153	1070	350
Dog NOAEL^b				
20 mg/kg (Male) (HED 667 mg)	400	182	2270	937
60 mg/kg (Female) (HED 2000 mg)	13,700	2200	45,500	5930
Rat NOAEL^c				
15 mg/kg (injection site reaction) (HED 145 mg)	923	138	7,175	1,019
50 mg/kg (Systemic) (HED 484 mg)	17,900	1,345	141,500	8,930

^a human AUC and C_{max} values are estimated from projected PK at each dose level

^b NOAEL in dogs based on ophthalmic clinical observations at 60 mg/kg in males and no adverse toxicity in females. AUC values are AUC_{last}

^c NOAEL in rats based on adverse injection site reactions at 50 mg/kg, but no adverse target organ (systemic) toxicity at up to 50 mg/kg. AUC_{last} and C_{max} are means of male and female values.

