6 STUDY DRUG

6.1 STUDY DRUG(S) ADMINISTRATION

6.1.1 Study Drug Description

AMDX-2011P, a retinal tracer (small molecule), is a phosphate prodrug hydrolyzed in vivo to the pharmacologically active molecule AMDX-2011.

	Active
Study Drug Name (INN)	AMDX-2011P
Type	Retinal tracer (small molecule)
Dose Formulation	Solution for injection
Unit Dose Strength(s)	mg
Dosage Level(s)	
 • Cohort 1 – 25 mg (1 mL) • Cohort 2 – 50 mg (2 mL) • Cohort 3 – tentative 100 mg (4 mL) • Cohort 4 – tentative 150 or 200 mg (6-8 mL) 
For Cohorts 3-4, doses to be confirmed by SMC based on emerging data from prior cohorts. Intermediate and/or higher dose levels may be explored.

Route of Administration	IV bolus injection over 2 minutes
Use	Experimental
Sourcing	The drug product is manufactured by Pace (Salem, NH), and provided centrally by the Sponsor or subsidiary, or designee.
Preparation	Individual doses of AMDX-2011P will be prepared by pharmacy staff and will be provided to study personnel for administration. Procedures relating to study drug preparation will be outlined in the Pharmacy Manual. AMDX-2011P will be provided frozen (at -20°C) in a 10 mL amber vial containing 5.5 mL of solution at a concentration of 25 mg/mL. It is a single dose vial. Vials must not be shared between subjects. The solution is light sensitive and must be protected from light at all times. AMDX-2011P must be thawed to room temperature prior to administration; once thawed, it must be used within 3 hours.
Post administration instructions	Subjects to be instructed to avoid direct sun and wearing light protective eye gear such as sunglasses for 24 hours after the dose. Subjects will be evaluated for signs and symptoms of phototoxicity.
Packaging and Labeling	The study drug will be dispensed in single administration vials. Study drug will be labeled as required per local regulations. All packaging and labeling operations for the study drug will be performed according to

	Active
	current Good Manufacturing Practices and the relevant regulatory requirements.
Storage Condition	Study drug is to be stored in a secure freezer (-20°C) and monitored (manual or automated) in accordance with the labeled storage conditions with access limited to the investigator and authorized site staff.

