8.2 SAFETY AND OTHER ASSESSMENTS

Safety assessments will include physical examination, ophthalmologic examination, vital signs, electrocardiogram (ECG), and laboratory assessments. Adverse events and concomitant medications will be monitored throughout the study.

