8.2.1 Physical Examinations

- A complete physical examination will include, at a minimum, assessment of the Cardiovascular, Respiratory, Gastrointestinal, and Neurological systems.
- Height and body weight will be measured and recorded at screening.
- Investigators should pay special attention to clinical signs related to previous serious illnesses.

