8.4.3 Classification of an Adverse Event

8.4.3.1 Severity of Event

AE severity will be evaluated by the investigator in accordance with the National Cancer Institute (NCI) CTCAE v5.0¹. For AEs that are not adequately addressed in the NCI CTCAE, the investigator should classify the intensity of the AE using the following guidelines:

- Grade 1: Mild: Aware of sign or symptom, but easily tolerated; no intervention needed
- Grade 2: Moderate: Discomfort enough to cause interference with usual activity, minimal non-invasive intervention indicated (e.g., short course of antibiotics)
- Grade 3: Severe: Medically significant but not immediately life-threatening; incapacitation with inability to work or do usual activity
- Grade 4: Life-threatening: Refers to an event in which the subject was at risk of death at the time of the event, as judged by the investigator; urgent/emergent intervention indicated. This category should not be used for an event that hypothetically might have caused death if it were more severe.
- Grade 5: Fatal outcome.

¹ Please refer to the CTCAE v5 at:

https://ctep.cancer.gov/protocolDevelopment/electronic_applications/docs/CTCAE_v5_Quick_Reference_5x7.pdf. Accessed March 30, 2022

It will be left to the investigator's clinical judgment to determine whether an AE is of sufficient severity to require the subject's removal from treatment or from the study. A subject may also voluntarily withdraw consent from treatment due to what she/he perceives as an intolerable AE. If either of these situations arises, the subject should be strongly encouraged to undergo an EOS assessment and be under medical supervision until symptoms cease or the condition becomes stable. An event is defined as 'serious' when it meets at least 1 of the predefined outcomes as described in the definition of an SAE, NOT when it is rated as severe.

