8.4.4 Time Period and Frequency for Event Assessment and Follow-Up

The occurrence of an AE or SAE may come to the attention of study personnel during study visits and interviews of a study subject presenting for medical care, or upon review by a study monitor.

All AEs including local and systemic reactions not meeting the criteria for SAEs will be captured on the appropriate eCRF. Information to be collected includes event description, time of onset, clinician's assessment of severity, relationship to study product (assessed only by those with the training and authority to make a diagnosis), and time of resolution/stabilization of the event. All AEs occurring while on study must be documented appropriately regardless of relationship. All AEs will be followed to adequate resolution.

Any medical condition that is present at the time that the subject is screened will be considered as baseline and will be reported in the Medical History eCRF page, not as an AE. However, if the study subject's condition deteriorates at any time during the study, it will be recorded as an AE.

Changes in the severity of an AE will be documented to allow an assessment of the duration of the event at each level of severity to be performed. AEs characterized as intermittent require documentation of onset and duration of each episode.

The investigator will record all events with start dates occurring any time after informed consent is obtained until 7 days after the study drug administration for non-serious AEs or 30 days after the study drug administration for SAEs. At each study visit, the investigator will inquire about the occurrence of AE/SAEs since the last visit. Events will be followed for outcome information until resolution or stabilization.

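### No post-dose inspection of the injection site is scheduled, although injection-site reactions are a named risk, set the rat NOAEL and feed the primary adverse-event endpoint

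*Protocol*

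**What the plan says.** **Risk.** Protocol Table 2 (Section 2.3.1) lists injection-site reactions as a procedure-related risk. Its mitigation is trained staff, with observation and treatment if a reaction occurs. Section 2.1 reports the animal basis: "Injection site reactions occurred in rats after administration into the tail vein, which were considered adverse at 50 mg/kg". Table 4 (Section 4.3) carries the rat NOAEL for this finding as "15 mg/kg (injection site reaction) (HED 145 mg".

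**Scheduled assessments.** Section 8 refers to Table 1 (Section 1.3) for procedures and their timing. Table 1 places the physical examination at Screening and adds "On Day 1, PE may be repeated if abnormalities are detected at screening". Section 8.2 gives the safety list: "Safety assessments will include physical examination, ophthalmologic examination, vital signs, electrocardiogram (ECG), and laboratory assessments". Section 8.2.1 sets the content of the examination: "A complete physical examination will include, at a minimum, assessment of the Cardiovascular, Respiratory, Gastrointestinal, and Neurological systems". SAP Section 6.7.2 describes a screening examination and has no skin or injection-site item.

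**Phototoxicity.** Table 2 has a general phototoxicity row, and Section 6.1.1 says "Subjects will be evaluated for signs and symptoms of phototoxicity". It gives no time point and no body site.

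**Adverse-event capture.** Section 8.4.4 requires an inquiry at each visit and states "All AEs including local and systemic reactions not meeting the criteria for SAEs will be captured on the appropriate eCRF". Section 8.4.3.1 sets the grading: "AE severity will be evaluated by the investigator in accordance with the National Cancer Institute (NCI) CTCAE".

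**The concern.** The primary endpoint is the incidence, nature and severity of adverse events (Protocol Section 3). Of the data types that Section 4.1 names for the escalation review (adverse events, ECGs, vital signs, laboratory results), only adverse events would carry a local finding.

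For a local toxicity already seen in animals, the plan relies on the subject mentioning it or on staff happening to notice it. A count of zero reactions could then mean that none occurred, or that nobody looked. Mild redness or swelling is the kind of sign most easily lost this way. At stake is how accurately mild local reactions are described, mainly at the highest dose.

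**Working it through.** **Step 1. Post-dose looks in the schedule.** The post-dose entries in Table 1 are eye examination, vital signs, ECG, safety laboratories, urinalysis, urine pregnancy test (Day 8), adverse-event reporting, concomitant medications, retinal imaging and PK sampling. None is an inspection of the injection site or skin.

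- Scheduled post-dose physical examinations: 0. The Day 1 repeat is optional and depends on a screening abnormality, not on dosing.
- Scheduled post-dose inspections of injection site or skin: 0 on Day 1 and 0 on Day 8.
- The system list in Section 8.2.1 is a minimum and could be extended to skin, but there is no post-dose examination to which it would apply.

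**Step 2. Contacts that exist.** Day 1 includes 8 hours of confinement with 9 post-dose PK draws, 5 post-dose vital-sign sets and 2 post-dose triplicate ECG time points. One sentinel per cohort is evaluated at 24 hours, with content unspecified. If all four cohorts enroll, that is 4 subjects. The other 26 to 32 (30 − 4 to 36 − 4) have no scheduled visit between discharge and Day 8.

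**Step 3. Dose against the rat injection-site NOAEL.** Formula: planned dose divided by the 145 mg HED in Table 4.

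| Dose (mg) | Dose / 145 |
|---|---|
| 25 | 0.17 |
| 50 | 0.34 |
| 100 | 0.69 |
| 150 | 1.03 |
| 200 | 1.38 |

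Only Cohort 4 exceeds 1. Its share of subjects is 12/36 = 33% to 12/30 = 40%. The 30 is the sum of the cohort minimums (3 + 3 + 12 + 12), and 36 is the stated cap.

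**Step 4. The other animal comparators.**

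- Rat dose with adverse reactions, 50 mg/kg (HED 484 mg): 150/484 = 0.31; 200/484 = 0.41.
- Dog top dose, 60 mg/kg (HED 2000 mg), where injection-site findings were histologic and judged not adverse: 150/2000 = 0.075; 200/2000 = 0.10.
- Starting-dose margin: 484/25 = 19.4 against the rat systemic NOAEL, which matches the stated margin of about 20, but 145/25 = 5.8 against the injection-site NOAEL.

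**Step 5. Weight of one missed subject.** The change in observed incidence is 1/n: 1/12 = 8.3 percentage points, 1/9 = 11.1, and 1/3 = 33.3 (3 subjects is the minimum for an escalation review). These figures show leverage. They do not estimate how many would be missed.

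**The case against.** The case for leaving the plan alone is substantial.

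- **Detection is already good.** A 2-minute bolus by trained staff is followed by 8 hours of frequent contact, and capture of local reactions is mandatory. Itching and tenderness, two of the four signs in Table 2, are mainly found by asking. This stands for noticeable reactions. It does not create a required look for mild visible ones.
- **The animal signal is mixed.** The dog findings were not adverse, the rat route was the tail vein, and 150 mg exceeds 145 mg by only 3%. HED is a body-size conversion, whereas local reactions may also depend on concentration and volume (25 mg/mL, 6 to 8 mL); the rat concentration is not given. A reader might infer that Cohort 4 is predicted to produce adverse local reactions. The documents do not support that.
- **Escalation.** A reader might infer that dose decisions are compromised. The planned escalations follow Cohorts 1 to 3, at 0.17 to 0.69 of the HED, and Cohort 4 is the last planned dose. The stopping rules in Section 7.1 turn on related Grade 3 events, related serious events or poor tolerability, which mild local signs are unlikely to trigger.
- **Skin.** A reader might infer that cutaneous phototoxicity is a separately named risk left unmonitored. Table 2 names phototoxicity in general, skin appears there only as a negative rat result up to 50 mg/kg, and Section 6.1.1 does require an evaluation. The absent time point is missing detail, secondary to the injection-site gap.
- **Added noise.** Inspection after repeated blood draws, with no comparator arm, could put needle marks into the primary endpoint. This is a fair warning, and the fix has to exclude them.

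The study manuals and eCRF are not part of the documents and may contain prompts. That cannot be confirmed.

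**Conclusion.** The gap is real and modest. The protocol and SAP schedule no post-dose inspection for a named local risk that set the rat NOAEL, and the top planned dose is 1.03 to 1.38 times the corresponding HED. Recording a reaction once noticed is covered; looking for it is not. The likely effect is under-recording of mild injection-site signs, most relevant to the 12 subjects in Cohort 4.

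This rests on three assumptions: Table 1 is the full schedule, Cohort 4 is dosed at 150 or 200 mg, and some mild signs would be neither mentioned nor noticed. The size of the under-recording cannot be estimated from the documents. A change is worthwhile because it is cheap and replaces passive with active ascertainment in a first-in-human study, not because subject safety or dose decisions are shown to be at risk.

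**What to change.** Add one row to Protocol Table 1: a brief inspection of the study-drug injection site and exposed skin at four points:

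- predose
- before Day 1 discharge
- at the sentinel's existing 24-hour evaluation
- on Day 8

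State that this row carries out the phototoxicity evaluation in Section 6.1.1. Record findings at the dosing site that are new since predose, and suspected phototoxic skin findings, as adverse events under the existing CTCAE grading and dose-level summaries. Note the dosing site on the eCRF, and state that expected venipuncture or cannula marks at PK sampling sites are not counted as drug reactions.

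The cost is one eCRF page, a few minutes at contacts that already exist, and possibly a slightly higher count of mild adverse events. Two limits remain. In non-sentinel subjects, reactions that appear and resolve between discharge and Day 8 would still rely on recall. Inspection by unmasked investigators would not remove any dose-related reporting bias.
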